APPENDIX C

Application Site Reactions

Monitoring of local tolerability (inflammation) will be based upon established methods including observation of the area of administration and response scoring by the study personnel. Upon the visits to the clinical study site, each patient will be examined for signs of local inflammation and irritation that may be associated with the study products. If any such signs are identified, the response will be graded as follows:

Signs and Symptoms:

Erythema (redness)

Scaling/Dryness

Stinging/Burning

Erosion

Edema (swelling)

Pain

Itching

Grading Scale:

Absent 0

Mild 1 (slight, barely perceptible)

Moderate 2 (distinct presence)

Severe 3 (marked, intense)

Application site reactions will not be separately recorded as AEs since they are being captured at each visit for erythema, burning/stinging, erosion, edema, pain, itching or dryness unless the Investigator feels it is appropriate to do so.

A Randomized, Placebo-Controlled, Double-Blind, Parallel-Group, Multi-Site Phase 2b Clinical Study to Assess the Efficacy, Safety and Tolerability of 8-Week Regimens of Novexatin®, 10% Topical Solution (Taro Pharmaceuticals, USA, Inc.) in Patients with Mild to Moderate Onychomycosis

APPENDIX D

Safety Laboratory variables

Hematology

Hemoglobin
Hematocrit
Red blood cell count (RBC)
White blood cell count (WBC)
Mean corpuscular volume (MCV)
Mean corpuscular hemoglobin concentration (MCHC)
Platelet count
Differential white blood cell count
Mean corpuscular hemoglobin (MCH)

Clinical Chemistry

Sodium
Potassium
Calcium
Creatinine
Blood Urea Nitrogen (BUN)
Fasting Glucose
Albumin
Total Bilirubin
Alkaline phosphatase
Gamma-glutamyltransferase(GGT)
Aspartate aminotransferase (AST, SGOT)
Alanine aminotransferase (ALT, SGPT)
Total protein
Direct Bilirubin

Urinalysis

Bilirubin
Glucose
Ketone
Leukocyte Esterase
Nitrite
Occult Blood
pH
Protein
Specific Gravity
Urobilinogen

A Randomized, Placebo-Controlled, Double-Blind, Parallel-Group, Multi-Site Phase 2b Clinical Study to Assess the Efficacy, Safety and Tolerability of 8-Week Regimens of Novexatin®, 10% Topical Solution (Taro Pharmaceuticals, USA, Inc.) in Patients with Mild to Moderate Onychomycosis

APPENDIX E

Investigator Brochure for Novexatin®

A Randomized, Placebo-Controlled, Double-Blind, Parallel-Group, Multi-Site Phase 2b Clinical Study to Assess the Efficacy, Safety and Tolerability of 8-Week Regimens of Novexatin®, 10% Topical Solution (Taro Pharmaceuticals, USA, Inc.) in Patients with Mild to Moderate Onychomycosis

APPENDIX F

AMENDMENTS TO THE PROTOCOL

Revisions to the protocol after initial IRB approval are summarized in the amendment below.

Amendment	Date
1	02/24/2016

The following revisions were made to the protocol dated 1/13/2016.

- Updated study schematic to reflect revised procedures
- Updated the study population information.
- Updated the Inclusion/Exclusion verbiage
- Updated the study conduct to include the Planimetry Assessment
- General administrative, formatting and spelling changes made throughout the protocol.
- Updated the restricted medication information and washout timeframes
- Updated the statistical section to include the planimetry involvement.
- Updated procedures for early termination patients.
- Removed the usage of an “Independent Dispenser” throughout the protocol.
- Updated the Identity of Investigational Product
- Updated the verbiage in Study Blind section.
- Updated the study procedures to include Planimetry and Application Site Reaction.
- Updated the verbiage of dosing compliance
- Updated the nail appearance grading scale
- Updated the KOH visit scheduling requirements.
- Minor updates made to the statistical sections to clarify the use of planimetry.
- Addition of Investigator Clinical Assessment description to study procedures
- Added “Place all records/ documents in patient’s source folder” to visits 5, 6 and 7 to be consistent with previous visits.
- Revised application site reactions scale and revised associated verbiage accordingly.

Amendment	Date
2	06/24/2016

The following revisions were made to the protocol dated 02/24/2016.

- Updated the Efficacy Endpoint verbiage
- Updated the Safety Endpoint verbiage

A Randomized, Placebo-Controlled, Double-Blind, Parallel-Group, Multi-Site Phase 2b Clinical Study to Assess the Efficacy, Safety and Tolerability of 8-Week Regimens of Novexatin®, 10% Topical Solution (Taro Pharmaceuticals, USA, Inc.) in Patients with Mild to Moderate Onychomycosis

- Updated the verbiage for the Sample Size Determination
- Updated the Statistical Analysis verbiage throughout the protocol.
- Updated Study Schematic to reflect revised procedures
- Updated the verbiage throughout the protocol to allow for bilateral toenail infections to be evaluated for all Visit 1 procedures.
- Updated verbiage to determine the target toenail at Visit 2.
- Updated verbiage to the Early Terminations and Protocol Deviations section.
- Updated verbiage to the Identify of the Investigational Product.
- Updated Study Conduct and Study Procedure sections to reflect updated procedures.
- General administrative, formatting and spelling changes made throughout the protocol.
- Updated the Study Procedures verbiage
- Updated verbiage to Appendix B to reflect updated procedures.

A Randomized, Placebo-Controlled, Double-Blind, Parallel-Group, Multi-Site Phase 2b Clinical Study to Assess the Efficacy, Safety and Tolerability of 8-Week Regimens of Novexatin®, 10% Topical Solution (Taro Pharmaceuticals, USA, Inc.) in Patients with Mild to Moderate Onychomycosis

**NOVUM PHARMACEUTICAL RESEARCH SERVICES**  
**STATISTICAL ANALYSIS PLAN**

**Novexatin 10% topical solution**

**Protocol / Study No. NVXT 1404/71442603**

**Revision History**

| VERSION   | DATE              | DESCRIPTION OF REVISIONS  | REVISED BY  |
|-----------|-------------------|---|-------------|
| Draft 1.0 | March 20, 2017    | New Document  | [name] |
| Draft 2.0 | December 12, 2017 | Incorporate Novum's comments  | [name] |
| Final 1.0 | February 26, 2018 | Add additional analyses, incorporate client comments and finalize SAP                         | [name] |
| Final 2.0 | March 1, 2018     | Add summary table T14.3.10 Summary of Frequency of Evaluation of Toenail Condition/Appearance | [name] |
| Final 3.0 | March 21, 2018    | Incorporate client's comments   | [name] |

**NOVUM PHARMACEUTICAL RESEARCH SERVICES  
STATISTICAL ANALYSIS PLAN**

**Novexatin 10% topical solution**

**Protocol / Study No. NVXT 1404/71442603**

**List of Abbreviations and Definition of Terms**

|        |  |
|--------|--|
| ADaM   | Analysis Data Model                            |
| AE     | Adverse Event                                  |
| ANCOVA | Analysis of Covariance                         |
| BP     | Blood Pressure                                 |
| C      | Celsius  |
| CRF    | Case Report Form                               |
| CDISC  | Clinical Data Interchange Standards Consortium |
| CRO    | Contract Research Organization                 |
| F      | Fahrenheit                                     |
| FDA    | Food and Drug Administration                   |
| HR     | Heart Rate                                     |
| Hg     | Mercury  |
| ICF    | Informed Consent Form                          |
| ICH    | International Conference on Harmonization      |
| IND    | Investigational New Drug                       |
| ITT    | Intent-to-Treat                                |
| LOCF   | Last Observation Carried Forward               |
| MedDRA | Medical Dictionary for Regulatory Activities   |
| OGD    | The Office of Generic Drugs                    |
| PP     | Per-Protocol                                   |
| SAE    | Serious Adverse Event                          |
| SAP    | Statistical Analysis Plan                      |
| SAS    | Statistical Analysis System                    |
| SDTM   | Study Data Tabulation Model                    |
| USA    | United States of America                       |

**Novexatin 10% topical solution**

**Protocol / Study No. NVXT 1404/71442603**

**1. INTRODUCTION**

This Statistical Analysis Plan (SAP) is based on the final Clinical Study Protocol NVXT 1404 (Novum Study No. 71442603) Rev. 2 dated July 8, 2016. The SAP provides details on the planned statistical methodology for the analysis of the study data. The SAP also outlines the statistical programming specifications for the tables, listings and figures.

This SAP describes the study endpoints, derived variables, anticipated data transformations and manipulations, and other details of the analyses not provided in the study protocol. This SAP therefore outlines in detail all other aspects pertaining to the planned analyses and presentations for this study.

The following documents were reviewed in preparation of this SAP:

- Final Clinical Study Protocol NVXT 1404 (Novum Study No. 71442603) Rev. 2 dated July 8, 2016
- Casebook for Novum Study No. 71442603 dated 11/30/2017

The reader of this SAP is encouraged to also read the clinical protocol for details on the conduct of this study, and the operational aspects of clinical assessments and timing for completing a patient in this study.

**2. OBJECTIVES**

1. Determine the rates of complete therapeutic cure of Novexatin® 10% topical solution (Taro Pharmaceuticals, USA) after daily dosing for one 8-week treatment period (Treatment Group A) and two 8-week treatment periods separated by a 32-week rest period (Treatment Group B), and Placebo (vehicle) topical solution (Taro Pharmaceuticals, USA) after two 8-week treatment periods separated by a 32-week rest period (Treatment Group C), at three test-of-cure visits (Day 141, Day 281 and Day 365) in patients with mild to moderate distal subungual onychomycosis of the target toenail.
2. Compare rates of complete therapeutic cure between Treatment Groups according to a hierarchical evaluation scheme detailed in the statistical sections.
3. Evaluate safety and tolerability of the two regimens of Novexatin® 10% topical solution (Treatment Groups A and B) in patients with mild to moderate distal subungual onychomycosis of the target toenail.

**3. OVERALL STUDY DESIGN**

This randomized, placebo-controlled, double-blind, parallel-group, multi-site study is designed to evaluate and compare the efficacy and safety of two dosing regimens of Novexatin® 10%

**NOVUM PHARMACEUTICAL RESEARCH SERVICES  
STATISTICAL ANALYSIS PLAN**

**Novexatin 10% topical solution**

**Protocol / Study No. NVXT 1404/71442603**

topical solution (Taro Pharmaceuticals USA) for the treatment of mild to moderate distal subungual onychomycosis of the target toenail. Additionally the active formulation in these regimens will be assessed for superiority to a placebo topical solution.

Up to 180 eligible patients with distal subungual onychomycosis who meet all the inclusion criteria and none of the exclusion criteria will be randomized into the study at Visit 2. Patients must be at least 18 years of age, in overall good health. They should have a current diagnosis of distal subungual onychomycosis of mild-moderate severity. Before any study-specific procedures are performed all patients will read and sign the IRB-approved informed consent form.

At least 60 qualified patients in each treatment group will receive randomized and blinded study product. The randomization scheme will be 1:1:1 (Active Treatment A: Active Treatment B: Placebo C). The study products are:

**Test:** Novexatin® 10% Topical Solution (Taro Pharmaceuticals, USA)

**Placebo:** Placebo (Vehicle) Topical Solution (Taro Pharmaceuticals, USA)

Patients will be assigned to one of the three treatment groups:

**Treatment Group A:** Test treatment for Days 1 – 56 and Placebo treatment for Days 281 – 336

**Treatment Group B:** Test treatment for Days 1 – 56 and Days 281 – 336

**Treatment Group C:** Placebo treatment for Days 1 – 56 and Days 281 – 336

Treatment and study durations will be as follows:

**Study Duration:** 365 days (52 weeks)

Patients will undergo evaluation for clinical and mycological cure of onychomycosis at the 7 clinic visits as per study schematic. Randomized patients who withdraw from the study will not be replaced. The study will be conducted according to the following schedule:

**Visit Schedule:**

- **Visit 1:** Days -35 to -1 (Screening)
- **Visit 2:** Day 1 (Baseline and Randomization / 1st Treatment start)
- **Visit 3:** Day 57 ± 4 (1st Treatment completion)
- **Visit 4:** Day 141 ± 7 (Interim)
- **Visit 5:** Day 281 ± 14 (2nd Treatment start)
- **Visit 6:** Day 337 ± 14 (2nd Treatment completion)
- **Visit 7:** Day 365 ± 14 (4 weeks post – treatment)

Unscheduled visits will be allowed as deemed necessary by Investigator.

**NOVUM PHARMACEUTICAL RESEARCH SERVICES  
STATISTICAL ANALYSIS PLAN**

**Novexatin 10% topical solution**

**Protocol / Study No. NVXT 1404/71442603**

The primary efficacy endpoint is the proportion of patients in each treatment group with a complete therapeutic cure of onychomycosis of the target toenail assessed at each of the two test-of-cure visits (Day 141 and Day 365). The safety profile of each treatment group will be evaluated by comparing adverse events, application site reactions, monitoring vital signs and changes in clinical laboratory results obtained throughout the study.

**NOVUM PHARMACEUTICAL RESEARCH SERVICES**  
**STATISTICAL ANALYSIS PLAN**

Novexatin 10% topical solution

Protocol / Study No. NVXT 1404/71442603

**Figure 1 Study Schematic**

| PROCEDURE   | Visit 1   | Visit 2  | Visit 3                              | Visit 4              | Visit 5                                      | Visit 6                              | Visit 7                                   |
|---|-----------|--|--------------------------------------|----------------------|--|--------------------------------------|---|
|   | Screening | Randomization / Baseline / 1 st treatment start | 1 st treatment completion | Interim Test of cure | 2 nd treatment start Test of cure | 2 nd treatment completion | 4 weeks post-treatment Test of cure or ET |
| Day   | -35 to -1 | 1  | 57 ± 4 (Week 8)                      | 141 ± 7 (Week 20)    | 281 ± 14 (Week 40)                           | 337 ± 14 (Week 48)                   | 365 ± 14 (Week 52)                        |
| Informed Consent  | X         |  |                                      |                      |  |                                      |   |
| Inclusion/ Exclusion Criteria Review  | X         | X  |                                      |                      |  |                                      |   |
| Demographics  | X         |  |                                      |                      |  |                                      |   |
| Medical History   | X         |  |                                      |                      |  |                                      |   |
| Physical Examination  | X         |  |                                      |                      |  |                                      | X   |
| Vital Signs   | X         |  | X                                    |                      | X  | X                                    | X   |
| KOH test  | X         |  |                                      | X                    |  |                                      | X   |
| Fungal Culture collection   | X         |  |                                      | X                    |  |                                      | X   |
| Clinical Lab Tests  | X         |  | X                                    |                      |  |                                      | X   |
| Target Nail trimming (if needed) before nail involvement/appearance assessments |           | X  | X                                    | X                    | X  | X                                    | X   |
| Target toenail involvement (assessed by visual assessment)*                     | X         | X  | X                                    | X                    | X  | X                                    | X   |
| Planimetry Assessment   |           | X  | X                                    | X                    | X  | X                                    | X   |
| Evaluation of toenail condition/appearance (by patient and investigator)        |           | X  | X                                    | X                    | X  | X                                    | X   |
| Investigator Clinical Assessment  | X         | X  | X                                    | X                    | X  | X                                    | X   |
| Urine Pregnancy Test**  | X         | X  | X                                    | X                    | X  | X                                    | X   |
| Dispense study product, supplies  |           | X  |                                      |                      | X  |                                      |   |
| Dispense Diary/Instructions   |           | X  | X                                    | X                    | X  | X                                    |   |
| Application site reactions  |           |  | X                                    | X                    | X  | X                                    | X   |
| Collect unused/empty bottle   |           |  | X                                    |                      |  |                                      | X   |
| Collect and Review Patient Diary  |           |  | X                                    | X                    | X  | X                                    | X   |
| Adverse Event Assessments   |           | X  | X                                    | X                    | X  | X                                    | X   |
| Concomitant Medication Review   | X         | X  | X                                    | X                    | X  | X                                    | X   |
| Schedule next visit   | X         | X  | X                                    | X                    | X  | X                                    |   |

\* At Visit 1, both toenails will be assessed if a bilateral infection of the big toenails are present.

\*\* All women of childbearing potential

**NOVUM PHARMACEUTICAL RESEARCH SERVICES  
STATISTICAL ANALYSIS PLAN**

**Novexatin 10% topical solution**

**Protocol / Study No. NVXT 1404/71442603**

**4. RANDOMIZATION AND BLINDING**

The study product will be packaged and blinded by an independent clinical packaging company. The randomization will be generated in blocks of 3, containing the study products in three configurations:

- A. bottles #1 & 2 – Test and bottles #3 & 4 – Placebo
- B. bottles #1 & 2 – Test and bottles #3 & 4 – Test
- C. bottles #1 & 2 – Placebo and bottles #3 & 4 – Placebo.

Three patients worth of study product bottles 1 & 2 will be packed into a larger box. This larger box will be designated “one block” of study product. The study product bottles 1 & 2 will be blinded, packaged and delivered to the study site in blocks at the beginning of the enrollment. Bottles 3 & 4 will be delivered to the study site before Visit 5 (2nd treatment start).

At each Visit 2 and Visit 5 each patient will receive two 5 ml bottles of study product according to the randomization code. Patients will be randomized to a treatment regimen in a blinded fashion by assigning randomization numbers in ascending sequential order starting with the lowest available randomization number at each site. All patients randomized will be identified by initials, date of birth, and a unique six-digit patient number. The first two-digits will identify the Investigator site where the patient was enrolled and the last four will correspond with the randomization number of study product bottle assigned to the patient. A perforated or two-part label will be attached to each of the small sized boxes of study product supplies. Both pieces of the label will include the following information: Protocol number, randomization number, space for patient’s initials, statement that the study product is for investigational use only, space for dispensing date and the Sponsor’s name. In addition all patients will be provided with written instructions on how to use the study product. One part of the label shall remain attached to the box. The other part will be removed prior to dispensing and attached to the study product log.

The Investigator, staff at the study site, study monitors, and data analysis/management personnel will be blinded to the patient assignment.

At the end of the study, after all the clinical data has been entered and the study database has been locked, a copy of the randomization will be sent to the statistician.

**5. SAMPLE SIZE**

The primary statistical analysis of interest is a comparison of the rates of therapeutic cure (as defined by "clinical cure" AND "mycological cure") of Novexatin® 10% topical solution to the rate of therapeutic cure of placebo in the Intent-to-Treat Population (ITT). The rate of therapeutic cure for the Novexatin® 10% topical solution 8-week regimens is expected to be approximately

**NOVUM PHARMACEUTICAL RESEARCH SERVICES  
STATISTICAL ANALYSIS PLAN**

**Novexatin 10% topical solution**

**Protocol / Study No. NVXT 1404/71442603**

49%. The rate of therapeutic cure for placebo is expected to be approximately 21%. Approximately 46 patients in each treatment group in the ITT population will provide over 80% power to show a difference at  $p < 0.05$  (two-sided Z test and a pooled response rate for the standard error of the difference in proportions) between each of the active treatment groups and the placebo group. To allow for a 23% drop-out rate, a total of 180 patients will be enrolled in the study, with up to 60 patients in each of the treatment groups.

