Safety Endpoints	
Adverse events will be classified using standard MedDRA terminology Version 19 or higher and summarized by treatment group. Adverse events reported during the study will be tabulated in a summary table listing the type, date of onset, date of resolution, incidence, severity, outcome, action taken, and Investigator's opinion of relationship to the study product. Signs and symptoms of onychomycosis will not be considered adverse events, unless in the Investigator's opinion, they have increased in frequency and/or severity to such an extent that the Investigator/patient considers that it is in the patient's best interest to be dropped from continued participation in the study and given alternative therapy for their onychomycosis.
 
If sufficient data exist, adverse event frequencies will be compared between treatments using Fisher's exact test or a similar test.
 
Concomitant medication use during the study will be tabulated by patient.

Sample Size Determination	
The primary statistical analysis of interest is a comparison of the rates (proportion of patients) of Complete Therapeutic Cure of Novexatin® 10% topical solution to the rate of Complete Therapeutic Cure of placebo in the Intent-to-Treat Population (ITT). The rates of Complete Therapeutic Cure for the Novexatin® 10% topical solution 8-week treatment regimens are expected to be approximately 49%. The rate of Complete Therapeutic Cure for placebo is expected to be approximately 21%. Approximately 46 patients in each treatment group in the ITT population will provide at least 80% power to show a difference at $p < 0.05$ (two-sided Z test and a pooled response rate for the standard error of the difference in proportions) between each of the active treatment groups and the placebo group. To allow for a 23% drop-out rate, a total of 180 patients will be enrolled in the study, with up to 60 patients in each of the treatment groups.

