10.6 Efficacy Analyses

The ITT population will be used to evaluate the efficacy of Novexatin® 10% topical solution for the 8-week treatment regimens in Groups A, B and C.

Descriptive statistics will be summarized for the primary and secondary endpoints (including planimetry data) by study group. As this is a multi-centered study, results may also be presented by study site.

In order to preserve an overall type-I error (alpha) of 5% for evaluation of complete and almost complete therapeutic cure, complete and satisfactory clinical cure and mycologic cure, a hierarchical evaluation scheme will be employed for the primary and secondary endpoints. The four comparisons of interest for the primary endpoint and the secondary endpoints -1 and -2 are:

1. Group B versus Group C – at the test-of-cure visit at Day 365
2. Group A versus Group C – at the test-of-cure visit at Day 365
3. Group B versus Group A – at the test-of-cure visit at Day 365
4. (Group A + Group B) versus Group C – at the test-of-cure visit at day 141

The five comparisons of interest for the secondary endpoints -3 and -4 are:

1. Group B versus Group C – at the test-of-cure visit at Day 365
2. Group A versus Group C – at the test-of-cure visit at Day 365
3. Group B versus Group A – at the test-of-cure visit at Day 365
4. (Group A + Group B) versus Group C – at the test-of-cure visit at Day 281
5. (Group A + Group B) versus Group C – at the test-of-cure visit at Day 141

A Randomized, Placebo-Controlled, Double-Blind, Parallel-Group, Multi-Site Phase 2b Clinical Study to Assess the Efficacy, Safety and Tolerability of 8-Week Regimens of Novexatin®, 10% Topical Solution (Taro Pharmaceuticals, USA, Inc.) in Patients with Mild to Moderate Onychomycosis

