Statistical testing will begin with comparison 1. If statistical significance is attained with comparison 1 ($p < 0.05$), then a claim of superiority for comparison 1 can be made and the next comparison in the hierarchical evaluation scheme can be tested for statistical significance. If statistical significance is not attained for comparison 1 ($p \geq 0.05$), then testing of all subsequent comparisons is stopped. The hierarchical, conditional-stepwise evaluation scheme allows for each comparison to be evaluated at the 5% level, while preserving an overall type I error rate of no more than 5%. For the proportion of patients in each treatment group with a complete and almost complete therapeutic cure, complete and satisfactory clinical cure and mycological cure of onychomycosis of the target toenail, the statistical analysis for superiority will be conducted using two-sided Z-Tests and a pooled response rate for the standard error of the difference in proportions for each comparison of interest. The primary and secondary analyses will be performed using an observed case (OC) analysis in the ITT population. Patients discontinued because of lack of treatment effect will be included in the primary analysis as treatment failures.

The following two sensitivity analyses will also be performed on the primary efficacy endpoint in the hierarchical, conditional-stepwise evaluation scheme:

1. Analysis will be performed also including patients without an assessment at Day 365 \pm 14. Patients with missing data at Day 365 \pm 14 will be considered therapeutic failures.
2. Analysis will be performed also including patients without an assessment at Day 365 \pm 14. Patients in Group C with missing data at Day 365 \pm 14 will be treated as therapeutic successes and patients from the Groups A and B with missing data at Day 365 \pm 14 will be treated as therapeutic failures.

Similar sensitivity analyses will be conducted including patients without an assessment at Day 141 \pm 7 for the 4th comparison in the hierarchical, conditional-stepwise evaluation scheme.

Efficacy results will be used to calculate the sample size for the Phase 3 studies.

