Statistical testing will begin with comparison 1. If statistical significance is attained with comparison 1 ( $p < 0.05$ ), then a claim of superiority for comparison 1 can be made and the next comparison in the hierarchical evaluation scheme can be tested for statistical significance. If statistical significance is not attained for comparison 1 ( $p \geq 0.05$ ), then testing of all subsequent comparisons is stopped. The hierarchical, conditional-stepwise evaluation scheme allows for each comparison to be evaluated at the 5% level, while preserving an overall type I error rate of no more than 5%. For the proportion of patients in each treatment group with a complete and almost complete therapeutic cure, complete and satisfactory clinical cure and mycological cure of onychomycosis of the target toenail, the statistical analysis for superiority will be conducted using a two-sided Cochran-Mantel-Haenszel (CMH) exact test, stratified by clinical site, at the 5% significance level. The primary and secondary analyses will be performed using an observed case (OC) analysis in the ITT population. Patients discontinued because of lack of treatment effect will be included in the primary analysis as treatment failures.

The following two sensitivity analyses will also be performed on the primary efficacy endpoint in the hierarchical, conditional-stepwise evaluation scheme:

**NOVUM PHARMACEUTICAL RESEARCH SERVICES  
STATISTICAL ANALYSIS PLAN**

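### The stated power of over 80% for each active group ignores the testing order: A vs C, tested only after B vs C succeeds, has about 71% at equal rates, and SAP 5 gives no power for the exact CMH test.

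*SAP*

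**What the plan says.** **Power statement.** SAP section 5 and protocol 10.2 state: "Approximately 46 patients in each treatment group in the ITT population will provide over 80% power to show a difference", using a two-sided pooled Z test at p < 0.05, "between each of the active treatment groups and the placebo group". The synopsis differs only in the strength of the claim: "Approximately 46 patients in each treatment group in the ITT population will provide at least 80% power to show a difference". All three therefore cover A vs C as well as B vs C.

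**Planning rates.** One rate is given for both regimens. SAP 5 says cure with the "topical solution 8-week regimens is expected to be approximately" 49%; placebo is put at about 21%. Enrolment is 180, up to 60 per group, to allow for 23% dropout.

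**Testing order.** In protocol 10.6 and SAP 8.2.1, comparison 1 is B vs C at Day 365. Comparison 2 is "Group A versus Group C – at the test-of-cure visit at Day 365". If comparison 1 has p ≥ 0.05, "then testing of all subsequent comparisons is stopped". The Table V shell in the SAP likewise withholds a p-value when the preceding one is 0.05 or more.

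**Test.** Protocol 10.6 specifies "two-sided Z-Tests and a pooled response rate for the standard error of the difference in proportions for each comparison of interest". SAP 8.2.1 and 8.7 replace this by "using a two-sided Cochran-Mantel-Haenszel (CMH) exact test, stratified by clinical site, at the 5% significance level". SAP 5 still describes the Z test.

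**The concern.** The plan contains no stand-alone A vs C test. A significant A vs C result requires two successes, B vs C first and then A vs C, so its power must be below that of a single test unless B vs C is almost certain to succeed. The sample size text nevertheless gives the single-test figure for each active group.

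Anyone relying on that text expects less than a 1 in 5 chance of missing significance for the one-course regimen when the planning rates are true. That expectation affects how a non-significant or untested A vs C result is read, in a study whose efficacy results are meant to size Phase 3. No estimate, p-value, test decision or type I error rate is affected.

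The change of test raises a smaller, separate question: the SAP's only power figure belongs to a test the SAP no longer plans to use.

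**Working it through.** **Inputs.** 46 per group, 49% in A and in B, 21% in C, two-sided 5%, pooled Z test, 23% dropout (SAP 5, protocol 10.2); 1:1:1 allocation (protocol 9.1, SAP 3); order and stopping rule (protocol 10.6, SAP 8.2.1).

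**Step 1: reproduce the plan's figure.**
- Pooled rate: (0.49 + 0.21)/2 = 0.35.
- SE under the null: √(2 × 0.35 × 0.65/46) = 0.0995.
- SE under the alternative: √((0.49 × 0.51 + 0.21 × 0.79)/46) = 0.0951.
- Power ≈ Φ((0.28 − 1.96 × 0.0995)/0.0951) = Φ(0.895) = 81.5%.
- Enumerating all binomial outcomes gives 81.6%.
- Enrolment: 46/(1 − 0.23) = 59.7, so 60 per group and 180 in total.

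The stated figure is correct for one ungated comparison.

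**Step 2: A vs C behind the gate.** The two tests share group C. For each number of cures c in C, let g_A(c) and g_B(c) be the probabilities that A vs C and B vs C are significant in favour of active treatment. Then

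P(both succeed) = Σ over c of P(c) × g_A(c) × g_B(c).

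At 46 per group and 49%/49%/21% this is **71.1%**. As a cross-check, a bivariate normal with correlation (0.21 × 0.79)/(0.21 × 0.79 + 0.49 × 0.51) = 0.1659/0.4158 = 0.40 gives 69.7%. Independent tests would give 0.816² = 66.5%, so the shared control helps but does not close the gap. The chance of missing A vs C is 100 − 71.1 = 28.9%.

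**Step 3: sensitivity to B's true rate** (A 49%, C 21%, 46 per group):

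| B's true rate | Gated power, A vs C |
|---|---|
| 46% | 65.0% |
| 49% (planned) | 71.1% |
| 52% | 75.5% |
| 55% | 78.3% |
| 60% | 80.6% |
| 70% | 81.5% |

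The ceiling is 81.6%, the power of A vs C alone.

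**Step 4: sensitivity to the number analysed** (49%/49%/21%):

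| Per group | Gated power, A vs C |
|---|---|
| 46 | 71.1% |
| 50 | 75.2% |
| 54 | 79.9% |
| 55 | 81.1% |
| 60 (no dropout) | 84.4% |

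Gated power first reaches 80% at 55 of 60 analysed, a loss of 5/60 = 8%, against the planned 23%.

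**Step 5: the exact test.** As a one-stratum reference only, Fisher's exact test at 46 per group gives 75.6% ungated and 63.0% gated. This is not the planned stratified test. Power of the exact CMH test depends on the number of sites, between-site variation, pooling of small sites and the definition of the two-sided p-value. Simulations over assumed values (1 to 20 equal sites, site logit SD 0 to 1.5, 23% random dropout, two readings of the 49%/21% rates, two p-value definitions) gave 58% to 88% for B vs C and 42% to 80% for gated A vs C. None of these assumptions is in the documents. The range shows that B vs C could fall on either side of 80%, and nothing more.

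**The case against.** The strongest reply is that the text states ordinary per-comparison power and names the test it used. It reproduces, and it makes no claim about reaching and winning A vs C in sequence; the gate is plainly set out elsewhere. On this view the text is incomplete, not wrong. The arithmetic point stands, but the text applies the figure to each active group without saying that it ignores the gate, and the planned procedure offers no ungated A vs C test to which it could apply.

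Second, B receives a second active course, and B vs A is itself a planned comparison, so B may do better than A. That is fair: the shortfall is small at B 55% and gone at B 60%. But the documents plan one rate for both regimens, and 60% is 11 points above it. If B is lower than planned, the shortfall grows.

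Third, more than 46 per group may be analysed, because patients who stop for lack of effect are kept as failures. That is possible, though added failures also lower the cure rates. The power claim itself is made at 46.

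Fourth, the SAP openly discloses and justifies the change of test, and SAP 5 does not say that its figure applies to the CMH test. This stands. The CMH point is a missing calculation, not a demonstrated loss of power.

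**Conclusion.** The concern holds. Under the stated Z test, with 46 analysed per group and true rates of 49% in A and B and 21% in C, power is 81.6% for B vs C and 71.1% for A vs C, about 10 points lower. The risk of missing A vs C is about 29% rather than under 20%. The 71% rests on equal true rates in A and B, which is the documents' own planning assumption. With A at 49% and B between 46% and 60%, it runs from 65.0% to 80.6%.

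The absence of a power figure for the exact CMH test is a secondary gap. No direction is claimed for B vs C under that test, and the main conclusion does not depend on it. The error is confined to the stated power, so this should be fixed but does not threaten the analysis.

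**What to change.** 1. In SAP 5, protocol 10.2 and the synopsis, state that the 80% figure is the power of a single ungated pooled Z-test comparison. Add that A vs C, tested only after B vs C has p < 0.05, has about 71% power under that Z test at 46 per group, assuming equal true rates of 49% in A and B.
2. In SAP 5 only, calculate power for B vs C and for gated A vs C under the planned exact CMH test. Report both as ranges and state the assumed number of sites, between-site variation, pooling and two-sided p-value definition. Protocol 10.2 needs no CMH figure, because the protocol specifies the Z test.

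The cost is a few sentences and one power calculation, with no extra patients and no change to the analysis. The drawback is a less favourable stated power for A vs C.
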